5.6 Prior and Concomitant Therapy

CONFIDENTIAL

If present, current antidepressant treatment (pharmacological, augmenting agents, and non-pharmacological) must be dose stable for at least 2 months prior to beginning the study. Patients will continue with current antidepressant treatment throughout the study. Based on our experience in current research at the VA Medical Center using serial ketamine dosing (Shiroma 2013), patients have shown positive results while continuing their current antidepressant treatment.

5.7 Packaging

Commercially available ketamine hydrochloride will be purchased 10 mL vials of 50mg/mL ketamine. Cartons of study drug vials will be purchased to ensure sufficient drug is available for at least five subjects at a time.

5.8 Blinding of Study Drug

Not applicable.

5.9 Receiving, Storage, Dispensing and Return

Receipt and Storage of Drug Supplies

The local site pharmacist will purchase and store the commercially available study drug. Ketamine must be stored between 20 and 25 degrees Celsius, and protected from light. Ketamine vials will be stored in carton until time of use.

Dispensing of Study Drug

The local site pharmacist will dispense the study drug, which will be openly labeled for investigational use only. Regular study drug reconciliation will be performed to document drug assigned, drug consumed, and drug remaining. This reconciliation will be logged on the drug reconciliation form, and signed and dated by the study team.

Return or Destruction of Study Drug

At the completion of the study, there will be a final reconciliation of drug shipped, drug consumed, and drug remaining. This reconciliation will be logged on the drug reconciliation form, signed and dated. Any discrepancies noted will be investigated, resolved, and documented prior to return or destruction of unused study drug. Drug destroyed on site will be documented in the study files.

6 Study Procedures

6.1 Visit 1 – Baseline assessment

As a first step, informed consent will be obtained from the parents/guardians of the adolescent and assent will be obtained from the adolescent by authorized members of the study team. If the adolescent is able to provide consent legally, such consent will be obtained from him/her. We will attempt to obtain consent from both parents except where it is not possible (e.g. death of a parent, parent does not have custody) or it is prohibitive to do so (e.g. parent lives in another state, parent is unavailable during reasonable business hours).

Demographic information will be obtained from the adolescent and the parent(s)/guardian(s) using “Ketamine Demographics Form”.

The adolescent and the parent(s)/guardian(s) will participate in a semi-structured diagnostic interview (the Kiddie Schedule for Affective Disorders and Schizophrenia, parent and lifetime version – K-SADS-PL). During this interview, a complete psychiatric history will be obtained for each participant. We will systematically evaluate the history of previous antidepressant trials using the Antidepressant Treatment History Form (Sackeim, 2001). Adolescent participants will complete a self-report Beck-Depression Inventory-II to assess depression severity as well as Snait-Hamilton Pleasure Scale (SHAPS) and Temporal Experience of Pleasure Scale (TEPS) to assess anhedonia severity. The clinician will complete a Children’s Depression Rating Scale-Revised, a clinical interview with both adolescent and parent/guardian (separately), to assess depression severity. Clinicians will also complete the Columbia Suicide Severity Rating Scale (CSSRS), Brief Psychiatric Rating Scale (BPRS) and Montgomery-Åsberg Depression Rating Scale (MADRS). Additionally, the clinician will also administer the two subset version of the WASI to estimate intelligence. Finally, the participant will be asked to complete DPX-task. If participants meet inclusion criteria they will be scheduled for the subsequent procedures. For participants that have not had a medical history and physical examination completed within the past 30 days, this will be completed at the end of the baseline visit by one of the medical doctors on the research team.

6.2 Visit 2 – MRI scan

Participants will be undergo an MRI scan before the first ketamine treatment and after the last ketamine treatment using a Siemens Prisma 3 Tesla scanner located in the University of Minnesota Center for Magnetic Resonance Research (CMRR). Before the scan, the parent/guardian will be asked to complete an MRI safety screening form for their child and the adolescent will be asked to provide a urine sample, which will be used to test for the presence of illicit drugs and (for females) pregnancy. If either result is positive, the participant will not be able to continue with the study. The scanning protocol will consist of two functional MRI scans (one during rest and one during an emotion task), a high-resolution T1-weighted anatomical image, and a diffusion tensor imaging sequence. Participants will be transported to the CMRR by their parents. If the participant is on the inpatient service, the treating physician will write a pass to allow the

family to take the patient for several hours to complete the scanning. If the study physician and/or the family do not feel that a pass would be appropriate due to safety concerns, the MRI visit will be waived.

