3.2 Primary Study Endpoints

The primary outcome measure is response status as defined by Children's Depression Rating Scale (CDRS) (Poznanski, 1985) Responders will be defined as having a significant reduction in their CDRS score ($\geq 50\%$) whereas non-responders will be defined as subjects whose scores do not show such a significant reduction or whose score increase. The percent change will be calculated by the formula below (Tao, 2009):

$$(\text{Baseline CDRS} - \text{Exit CDRS}) / (\text{Baseline CDRS} - 17)$$

Baseline CDRS: CDRS score obtained on Visit 1 – Baseline Assessment (Section 6.1)
Exit CDRS: the latest CDRS score obtained on Visit 10 - Clinical Assessment (Section 6.6) or Visit 11-16 – Follow-up Period (Section 6.7)

CONFIDENTIAL

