6.5 Visit 9 – Second brain MRI

Within 1 week of the last ketamine infusion, participants will undergo another brain MRI identical to the previous one (please see section 6.2 for more details).

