6.6 Visit 10 – Clinical assessment and blood draw

Also within one week of the last ketamine infusion, participants will come to the Ambulatory Research Center or participate in a phone or video conference for clinical evaluation to assess their clinical response to the ketamine infusions. At this visit, the following assessments will be completed to determine response to treatment: Columbia Suicide Severity Rating Scale – Since Last Visit (CSSRS-SLV), Montgomery-Asberg Depression Rating Scale (MADRS), Clinician-Administered Dissociative States Scale (CADSS), Profile of Mood States-Adolescent Version (POMS-A), Snaith-Hamilton Pleasure Scale (SHAPS), Temporal Experience of Pleasure Scale (TEPS), Beck Depression Inventory-II (BDI-II), Clinical Global Impression (CGI), and Brief Psychiatric Rating Scale (BPRS). Also, the clinician will complete a Children’s Depression Rating

CONFIDENTIAL

Scale-Revised, a clinical interview with both adolescent and parent/guardian (separately), to assess depression severity. The participant will also be asked to perform the DPX-task.

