6.7 Visits 11-16 – Follow-up period

All participants will be asked to speak with the research team for weekly follow-up visits for 6 weeks. Participants will continue to take medications as prescribed by their doctor. At each of these visits, participants will be asked about any medication changes and will complete the same assessments as administered in visit 10 (MADRS, CADSS, POMS-A, SHAPS, TEPS, BDI-II, CGI, CDRS and BPRS).

All participants will be asked to participate in the 6 weekly follow-up visits, regardless of response.

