7.2 Subject Population(s) for Analysis

Data from each participant who completes the six ketamine treatments will be subjected to the primary study analysis. We will conduct secondary analyses on all participants who received at least one dose of treatment.

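### The rule that a positive urine test ends participation is not confined to the first MRI, so read literally it can remove a participant after all six infusions and lose outcome data the plan needs

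*Combined protocol and SAP*

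**What the plan says.** Section 6.2 is headed as Visit 2, but its first sentence schedules "an MRI scan before the first ketamine treatment and after the last ketamine treatment". It then sets the check before scanning: "the adolescent will be asked to provide a urine sample, which will be used to test for the presence of illicit drugs and (for females)", where the second test is for pregnancy. The consequence follows directly: "If either result is positive, the participant will not be able to continue with the study".

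Section 6.5 places Visit 9 within a week of the sixth infusion and says that "participants will undergo another brain MRI identical to the previous one (please see section 6.2 for more details"). It makes no exception for the urine rule.

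Section 6.6 uses the same window for the clinical assessment: "Also within one week of the last ketamine infusion, participants will come to the Ambulatory Research Center", or be assessed by phone or video. No order between Visits 9 and 10 is stated.

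Four other sections bear on what happens next:

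- Section 3.2 defines the exit CDRS as "the latest CDRS score obtained on Visit 10 - Clinical Assessment (Section 6.6) or Visit 11-16 – Follow-up Period (Section 6.7").
- Section 6.7 says: "All participants will be asked to participate in the 6 weekly follow-up visits, regardless of response".
- Section 7.2 says: "Data from each participant who completes the six ketamine treatments will be subjected to the primary study analysis".
- Section 4.4 lists three grounds for withdrawal: intolerable side effects, failure to adhere to the protocol, and withdrawn consent. A positive urine test is not among them.

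**The concern.** Before the first infusion, a rule of this kind acts as an eligibility check and removes nobody from the treated population. At Visit 9 dosing is over. There, the same rule removes a participant whom Section 7.2 has already placed in the primary analysis, at about the time the post-treatment outcome is due. The missing data would then be produced by the protocol itself.

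The statistical plan (Sections 7.1 to 7.3) has no missing-data rule, so it does not say how such a completer would be counted. In a single-group study of 20, one or two participants of this kind matter. The scheduled weekly contacts would also stop for someone recently exposed to the study drug.

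**Working it through.** The plan has no figure of its own on this point to reproduce. The check is to follow one participant through the text and then size the loss.

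**Following the text for a participant who tests positive at Visit 9**

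1. *Does the 6.2 rule reach Visit 9?* Section 6.2 speaks of both scans, and the rule has no time limit. Section 6.5 refers back to 6.2 without exception. The schedule table in 6.8 has no column for the urine test, so it does not settle the question. On the literal text, the rule applies.
2. *Is there already a post-treatment CDRS?* Section 6.3, repeated for later infusions by 6.4, lists BDI-II, SHAPS, TEPS, POMS-A, CGI, BPRS, MADRS and CADSS at infusion visits. CDRS is not listed. Under 3.2 the exit CDRS can come only from Visits 10 to 16.
3. *What is lost?* This depends on an order that the protocol does not fix.
   - Visit 9 before Visit 10: no exit CDRS, no suicidality rating at Visit 10, and no weekly scores for time to relapse.
   - Visit 10 before Visit 9: one exit CDRS exists, so response status can be computed. The weekly visits are lost. Because 3.2 takes the latest score, this participant's exit value would also be fixed earlier than for participants who are followed.
4. *Which sections disagree?* Section 7.2 keeps this participant in the primary analysis. Section 6.7 asks for the weekly visits. Section 4.4 gives no matching withdrawal reason. Section 6.2 ends participation. They cannot all be followed.
5. *Would cancelling only the scan settle it?* Not fully. Section 5.5 counts attendance at two MRI scans as part of compliance and ends participation for non-compliance. The one MRI waiver, in 6.2, is for inpatients when a pass is judged unsafe.

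**Size**

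Input from the documents: n = 20 (Section 3.1). Assumption: all 20 complete six infusions.

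Share of the responder proportion left unknown by k participants without an exit CDRS = k/20:

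- k = 1: 1/20 = 5 points
- k = 2: 2/20 = 10 points
- k = 3: 3/20 = 15 points

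The documents give no positive-test rate. For assumed rates p, the chance of at least one positive among 20 is 1 − (1 − p)^20:

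- p = 2%: 1 − 0.98^20 = 33% (expected number 20 × 0.02 = 0.4)
- p = 5%: 1 − 0.95^20 = 64% (expected number 1)
- p = 10%: 1 − 0.90^20 = 88% (expected number 2)

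**Direction**

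Suppose, as an assumption, that 10 of 20 truly respond (50%) and that k participants are left out of the denominator.

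- All lost are non-responders: 10/19 = 53%, 10/18 = 56%, 10/17 = 59% for k = 1, 2, 3.
- All lost are responders: 9/19 = 47%, 8/18 = 44%, 7/17 = 41%.

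The sign depends entirely on who is lost, and the documents do not address that.

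**The case against.** The strongest reply is that the rule was never meant for Visit 9. It sits under the Visit 2 heading and speaks of one scan. In 6.5, the claim of identity attaches to the MRI and may mean only the imaging session. Pregnancy and recent substance abuse are entry exclusions in 4.2, which suits a pre-treatment check. The silence of 4.4 and the wording of 6.7 can equally be taken as evidence that treated participants were meant to stay. This may well be the intention, but no sentence says so, and staff following 6.2 and 6.5 as written would have grounds to end participation.

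A reader might go further and infer that fully treated participants are bound to leave before any post-treatment CDRS. The documents do not support that: Visits 9 and 10 share one window with no stated order, and Visit 10 may come first.

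A reader might also infer that all outcome and safety information is lost. That does not hold either. MADRS and BDI-II are taken two hours after each infusion, including the sixth. Adverse events are reportable to 30 days after the last dose (8.1), unresolved events are followed up (8.1), and 4.4 seeks a 6-month follow-up of all participants, with permission, that includes a CDRS-R. That late CDRS-R is not an exit score under 3.2, however, and none of these sources replaces the weekly CDRS needed for relapse.

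Finally, the analysis named as primary in 7.3 is a paired t test on the lowest post-treatment score, not a responder proportion. That is true, but 3.2 names response status as the primary outcome. If the t test is run on the CDRS, a participant with no post-treatment CDRS contributes no pair to it.

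**Conclusion.** The point holds as a contradiction in the text with a limited, conditional effect. Read literally, 6.2 with 6.5 ends participation after full treatment, against 4.4, 6.7 and 7.2. The certain loss for such a participant is the weekly follow-up. Loss of every qualifying exit CDRS follows only if Visit 10 has not yet taken place.

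The size is up to 5 percentage points of the responder proportion per participant, assuming 20 completers. Only participants who test positive at Visit 9 are affected, and how many to expect cannot be derived from the documents.

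It is tempting to conclude that the rule inflates the response rate, on the ground that drug use soon after treatment may go with poor response. That is plausible but not shown. A positive pregnancy test has no stated link to response, and the calculation moves either way with the assumption made. The correction is still worth making, because it prevents avoidable missing outcomes at almost no cost.

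**What to change.** Reconcile Sections 6.2 and 6.5 with 4.4, 5.5, 6.7 and 7.2 in a short amendment:

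- In 6.2 and 6.5, state whether the discontinuation rule applies only before the first infusion.
- In 6.5, state that outcome and safety data collection at Visits 10 to 16 continues for every treated participant, whatever the Visit 9 urine result.
- In 7.2, state that these participants stay in the analysis sets.
- In 5.5, state whether a second MRI not done because of the urine result counts as non-compliance. In 4.4, bring the withdrawal reasons into line with whatever 6.2 then says.

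Whether the Visit 9 scan goes ahead, and how a positive drug or pregnancy result is managed clinically, is for the sponsor to decide.

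The cost is a few sentences. Visits 10 to 16 are already scheduled, so no visit or assessment is added.

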4.1 Inclusion Criteria

Patients will be eligible to participate in the study if all of the following conditions exist:

- 1) Willing and able to provide informed consent and assent.
- 2) Male and female adolescents aged 12 to 18 years.
- 3) Presence of recurrent MDD confirmed by the K-SADS-PL (Kaufman et al., 1997).
- 4) Current depression severity measured by the Children's Depression Rating Scale (CDRS) (Poznanski, 1985) raw score greater than or equal to 36 at screening and the day ketamine is due to be received for the first time.
- 5) Current depressive episode resistant to treatment, defined as failure to achieve remission (elimination of symptoms and restoration of pre-morbid psychosocial functioning) from at least 2 antidepressant trials. Systematic evaluation of previous antidepressant trials will be assessed by using the Antidepressant Treatment History Form (Sackeim, 2001).
- 6) If present, current antidepressant medication treatment must be dose stable for at least 2 months prior to beginning the study*
- 7) Participants should have a medical history and physical examination in the 30 days prior to initiating the ketamine infusions.

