4.2 Exclusion Criteria

Patients will be excluded from participation in the study if any of the following conditions exist:

1. Inability to speak English
2. A history of Mental Retardation or Autism Spectrum Disorder
3. Current or lifetime diagnosis of schizophrenia, schizoaffective disorder, psychosis not otherwise specified (NOS).
4. Diagnosis of seizures or other neurological disorders.
5. Comorbid diagnosis of substance abuse or dependence within 6 months of assessment.

CONFIDENTIAL

6. Clinically unstable medical illness.
7. Current use of barbiturates, narcotics, or non-benzodiazepine hypnotics at doses higher than Zolpidem 10 mg or equivalent for insomnia.
8. For females: pregnancy.
9. Inability to undergo an MRI scan.
10. A Family History notable for having at least one first-degree relative with schizophrenia, schizoaffective disorder, psychosis not otherwise specified (NOS).

* If there has been a recent discontinuation of a medication, we will require lapses of time before study entry as follows: Antidepressants (excluding Fluoxetine) – 2 weeks; Fluoxetine – 4 weeks; Mood Stabilizers – 2 weeks; Antipsychotics – 2 weeks; Stimulants – 1 week.

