4.3 Subject Recruitment and Screening

Adolescents with treatment resistant depression who have been admitted to the adolescent mental health inpatient unit, who present to the University of Minnesota Psychiatry Adolescent Mood Clinic, or who are referred from outside clinicians, and who meet inclusion and exclusion criteria for the study, will be invited to participate.

Prior to enrollment, project staff selected to recruit for this study will screen review records from the hospital and clinical services noted above to determine potentially eligible adolescent participants. If an adolescent appears to meet basic criteria for the study (appropriate age and diagnosis), staff will then check the consent for treatment form in the patient's chart. If parents indicated on that form their willingness to have their child's medical records used in research, study staff will then contact the current treating provider to determine whether the provider feels it would be appropriate to invite this participant into the study. If so, the provider will request written permission of the adolescent and/or the parent for the study staff to contact them regarding the study. The study staff will then contact the parents by phone or in person to inform them about the purpose and activities of the current study.

We anticipate that some families will hear about our study through word of mouth or by searching on ClinicalTrials.gov. We will post information about the study in the community using flyers and online posting boards.

If after hearing about the study from study staff patients/families are interested in participating, the study staff will then conduct a screening form to ensure eligibility. If parents are interested and the adolescent is eligible, the first study visit will be scheduled. Informed consent will be obtained at the time of the first study visit.

CONFIDENTIAL

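### Waiving the Visit 2 MRI for some inpatients also removes the only pregnancy test and urine drug screen that the protocol specifies before dosing

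*Combined protocol and SAP*

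**What the plan says.** Section 6.2 describes Visit 2, the MRI before treatment. Before the scan the adolescent gives a urine sample, "which will be used to test for the presence of illicit drugs and (for females) pregnancy". The result decides whether the participant goes on: "If either result is positive, the participant will not be able to continue with the study".

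The section then deals with inpatients, who need a pass to leave the hospital for the scanner. "If the study physician and/or the family do not feel that a pass would be appropriate due to safety concerns", then "the MRI visit will be waived". Nothing further is said about the urine sample in that case.

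Three other parts of the protocol bear on this:

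- Section 4.2, exclusion 8, reads "For females: pregnancy", with no test method or timing.
- Section 4.3 names inpatients first among the recruitment sources: "Adolescents with treatment resistant depression who have been admitted to the adolescent mental health inpatient unit".
- Section 6.3 provides for inpatients to be taken by hospital staff to the infusion clinic, which is in the same building, and dosed there.

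**The concern.** The urine tests are a condition for receiving ketamine, but they are written as part of an imaging visit that some participants are allowed to skip. The reason for skipping it is the risk of leaving the unit. A urine sample does not require leaving the unit, so losing the tests is probably unintended.

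The main issue is participant protection. A female inpatient aged 12 to 18 whose scan is waived could receive up to six infusions without exclusion 8 having been verified by any specified test.

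A secondary issue is consistency. The rule that a positive drug screen ends participation would apply to scanned participants and not to those whose scan is waived.

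**Working it through.** No statistical calculation applies. The check is a count of where the protocol names a pregnancy test or a urine drug screen, from recruitment through the last infusion.

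| Section | What it provides | Pregnancy test named | Urine drug screen named |
|---|---|---|---|
| 4.1 Inclusion | History and physical within 30 days before the infusions | 0 | 0 |
| 4.2 Exclusion | Pregnancy (8) and recent substance diagnosis (5), no test stated | 0 | 0 |
| 4.3 Screening | Screening form | 0 | 0 |
| 6.1 Visit 1 | K-SADS-PL, rating scales, history and physical if not recent | 0 | 0 |
| 6.2 Visit 2 | Urine sample before the MRI | 1 (females) | 1 |
| 6.3 Visit 3, infusion 1 | Research blood draw, vital signs, rating scales | 0 | 0 |
| 6.4 Visits 4-8, infusions 2-6 | As Visit 3, apart from the blood draws | 0 | 0 |
| 6.8 Schedule | Six columns, none for either test | 0 | 0 |

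**Standard path.** Summing the columns gives 1 pregnancy test (females) and 1 drug screen before infusion 1.

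**Waived path.** Removing Visit 2 gives 1 − 1 = 0 pregnancy tests and 1 − 1 = 0 drug screens. Because Sections 6.3 and 6.4 add none, no specified test precedes any of the six infusions.

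Four possible substitutes were checked:

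- *Pre-infusion blood at Visit 3.* It is sent to an outside laboratory for the mechanistic assays described in Section 7.3 (gene expression, insulin signalling, cytokines). Neither section lists a pregnancy or toxicology assay.
- *Visit 9.* Section 6.5 makes the second MRI identical to the first, so a urine test may be repeated there, but only after all six infusions.
- *The abbreviation list.* A urine toxicology screen appears there with no procedure or timing attached.
- *The word pregnancy.* It occurs twice in the visible text, as exclusion 8 and as the Visit 2 test.

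**The case against.** The strongest reply is that nothing waives exclusion 8. The site must still establish that a participant is eligible, and staff could sensibly read the waiver as covering only the scan. Two checks also survive the waiver: at recruitment "the study staff will then conduct a screening form to ensure eligibility", and in Section 4.1 "Participants should have a medical history and physical examination in the 30 days prior to initiating the ketamine infusions". All of this is fair, and the protocol certainly does not permit dosing a pregnant participant. But neither check names a pregnancy test. History and interview depend on what the adolescent knows and discloses. The text waives the visit, and the urine sample is described only within that visit.

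A second reply is that the waived path may not be open at all. Exclusion 9 bars those unable to undergo MRI, and Section 5.5 requires attendance at two scans. These lines conflict with the waiver, but Section 6.2 is the specific provision and it excuses the visit without excluding the participant. In any case neither line restores the tests.

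A third reply is that the drug screen matters less. A positive screen is not an exclusion in Section 4.2; exclusion 5 rests on a diagnosis, which the Visit 1 interview still assesses. This stands in part. The pregnancy test carries most of the weight, and the drug screen is a matter of applying Section 6.2's own stopping rule evenly.

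Finally, the group may be very small, and there is no repeat test between infusions on the standard path either. Both are true. The difference between the paths is one baseline urine sample against none.

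**Conclusion.** The concern holds. In the visible protocol, Section 6.2 is the only place that names a pre-dose pregnancy test or urine drug screen, and its waiver removes both without relocating them. The difference is one of each test (pregnancy test in females only) on the standard path against none on the waived path.

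The conclusion rests on reading the waiver as written, and on the protocol text alone. The phone screen and the addendum assent for female minors listed in Section 14 were not available and might describe a check. Hospital admission testing might also cover some inpatients, but the protocol neither requires nor mentions it.

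The affected group is inpatients for whom the study physician or family judged a pass unsafe, and, for the pregnancy test, the females among them. The documents give neither the share of inpatients nor the frequency of waivers among the planned 20, so the number could be zero. There is no claim that the primary endpoint, the analysis or the sample size is affected. The case for acting is that a protection the protocol itself set is lost on a path the protocol itself provides, and can be restored at almost no cost.

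**What to change.** Amend Section 6.2 to say that waiving the scan does not waive the urine tests. Require the drug screen for every participant, and the pregnancy test for every female, before the first infusion; where the scan is waived, collect the sample on the ward or at the infusion clinic. List both tests in Section 6.8 separately from the MRI.

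The cost is a short amendment and one urine sample per waived participant. No extra visit is needed, because these participants are already on the ward and Visit 3 already includes a blood draw immediately before dosing.
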